3.3.3.3 Blinding

To minimize the risk of unblinding, all subjects will receive the same total volume for all treatments with no visible differences in the external appearance of treatments, infusion bags will be covered with a non-transparent sleeve, and opaque IV tubing will be utilized.

The unblinded study pharmacist, or designee, will prepare investigational product (i.e., AT-III [Human] and placebo) at each site. Monitoring of activated clotting time (ACT) for subject safety can potentially unblind an investigator if performed immediately before AND immediately after IP administration. Thus, to avoid potential unblinding, investigators should restrain from monitoring ACT values immediately before AND immediately after IP administration. Individual ACT determinations before OR after IP administration is not considered as potentially unblinding and is therefore permitted. However, if ACT monitoring is done prior to IP administration care must be taken to ensure blinded study personnel are not unblinded. Grifols Clinical Trial Materials personnel and Grifols Pharmacovigilance personnel will have access or be privy to treatment assignments.

Emergency unblinding instructions will be located in the Pharmacy Manual (to be used only if required).

Investigators must not draw any blood samples for AT levels outside the requirements of the protocol. Results from protocol-specified AT, TAT, and F1+2 measurements will not be provided to the Investigator or blinded sponsor personnel in order to ensure maintenance of the treatment blind.

3.3.3.4 Administration and Timing of Investigational Products for Each Subject

The dose of AT-III (Human) will be slowly administered, at a maximum rate of 0.1 mL/kg/min (minute), intravenously. The initial rate will be 0.05 mL/kg/min during the first 5 minutes, accelerating to 0.1 mL/kg/min if tolerated. Intolerance (the inability to provide the subject one full dose) of an infusion due to allergic reactions and anaphylactic symptoms may require decreasing or stopping the infusion rate of the product. In these instances, the following algorithm will be employed:

Severe reaction: Stop infusion. If symptoms subside, it will be at the physician's discretion whether to restart the infusion. The infusion may be restarted under careful nursing monitoring at one-half the previous rate. Appropriate concomitant medication may be given as directed by the physician based on the clinical evaluation.

Moderate reaction: Stop the infusion until all symptoms resolve. If resolution occurs in less than 30 minutes, the infusion may be restarted under careful nursing monitoring at one-half the previous infusion rate. Appropriate concomitant medication may be given as directed by the physician based on the clinical evaluation.

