3.3 Treatments

3.3.1 Treatments to Be Administered

3.3.1.1 AT-III (Human)

Detailed information of AT-III (Human) is also available in the IB.

AT-III (Human), a freeze-dried preparation for intravenous (IV) administration, has AT as the active ingredient. It is obtained from human plasma by a continuous purification process, which is performed in an authority-regulated plant in Clayton, North Carolina. Antithrombin is the main inhibitor of blood coagulation.

AT-III (Human) is prepared from pooled units of human plasma from normal donors by modifications and refinements of the cold ethanol method of Cohn. When reconstituted with sterile water for injection (SWFI), USP, AT-III (Human) has a pH of 6.0–7.5, a sodium content of 110–210 mEq/L, a chloride content of 110–210 mEq/L, an alanine content of

0.075–0.125 M, and a heparin content of not more than 0.1 IU heparin/IU ATIII. AT-III (Human) contains no preservative and must be administered by the IV route.

AT-III (Human) preparation will be reconstituted in 10 mL SWFI, which will be transferred into the vial containing the concentrate.

Usually the solution is clear or slightly opalescent. Do not use solutions that are cloudy or have deposits. Infusion of AT-III (Human) should be started within 3 hours of study drug reconstitution. It should be kept at room temperature not to exceed and precautions must be taken to avoid microbiological contamination. It should not be stored in the refrigerator or mixed with other drugs. Leftover product must never be kept for later use.

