3.3.2 Rationale for Selection of Doses/Timing of Investigational Products in the Study

3.3.2.1 Study Drug Doses

Every subject allocated in the AT-III (Human) treatment group will receive, immediately after anesthesia induction, a single dose of AT-III (Human) sufficient to achieve an absolute increase (Δ) of 20% (percentage points) above pretreatment AT levels according to the formula:

$$AT - III \text{ dose (IU) required} = \frac{(20) \times (\text{subject weight in kg})}{1.4}$$

The only variable in the equation is the subject's body weight. For calculating AT-III (Human) dose, subject's weight obtained during the Screening visit will be used.

AT-III (Human) or Placebo (0.9% NaCl) will be prepared according to the volume calculated by unblinded pharmacist or designee and will be infused intravenously.

AT-III (Human) will not be administered postoperatively unless the Investigator decides otherwise for clinical reasons (if this is the case, the subject will be excluded from the efficacy analysis).

After the operation, all subjects will be admitted to the ICU and will be followed for approximately 1 month regardless of when the ICU discharge takes place (see [Section 3.6.2](#)).

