3.3.3.5 Treatment Compliance

Treatment compliance will be measured only in terms of the subject receiving an infusion of AT-III (Human) from the study personnel. No other measure of treatment compliance will be employed.

Reasons for any deviation from the administration of less than 100% of the investigational product dose as prepared by the pharmacist, or designee, must be recorded in the electronic case report form (eCRF) and in the subject's medical records.

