3.8 Removal of Subjects

Subjects may withdraw or be withdrawn from the study for the following reasons:

1. At their own request or at the request of their legally acceptable representative.
2. If, in the Investigator's opinion, continuation in the study would be detrimental to the subject's well-being.

3. At the specific request of the sponsor.

Subject participation in the study may be terminated early under the following circumstances:

1. The subject withdraws his/her informed consent to participate in the clinical trial.
2. The subject does not meet all inclusion criteria and is deemed a screen failure.
3. The subject meets any of the exclusion criteria and is deemed a screen failure.
4. The subject is not able to adhere to the main protocol requirements (major protocol violations).
5. The occurrence of an AE, which in the Investigator's opinion requires the withdrawal of the subject from the clinical trial.
6. The subject is lost to follow-up.
7. Subject's death.
8. Subjects with an occurrence of a concomitant disease, or any medical condition which, either because of its severity or duration or necessary change in treatment, contravenes the condition of the study or puts the subject at unnecessary risk or harm per Investigator discretion.
9. Subjects who develop an infection with HAV, HBV, HCV, B19V, or HIV during the study. A subject should be withdrawn if, in the opinion of his/her physician, he/she develops any of these viral infections.
10. Any event, which in the opinion of the Investigator impedes the subject's participation in the study.

If the reason for early discontinuation is an AE, in so far as is possible, the subject will be followed-up until the event resolves, or has been stabilized, and no further change is expected.

In all cases, the reason for withdrawal must be recorded in the eCRF and in the subject's records.

A subject may leave the study at any time for any reason and will be permitted to do so without penalty. Grifols Therapeutics, Inc. will be notified by the Investigator if a subject terminates or is terminated from the study early. The reason for early termination will be clearly documented in the eCRF and reasonable efforts to perform study completion procedures will be made when appropriate. The Investigator can withdraw a subject from the clinical trial at any time.

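### Protocol 3.3.3.4 fixes restart conditions (all symptoms resolved, in under 30 minutes) after a moderate infusion reaction, but leaves restart after a severe one to symptoms subsiding and the physician's discretion

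*Protocol*

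**What the plan says.** Protocol 3.3.3.4 first sets the infusion rates: "The initial rate will be 0.05 mL/kg/min during the first 5 minutes, accelerating to 0.1 mL/kg/min if tolerated". It then gives an algorithm for subjects who cannot take the full dose because of allergic reactions or anaphylactic symptoms.

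- Severe branch: the infusion is stopped. Once symptoms have subsided, the treating physician has "discretion whether to restart the infusion. The infusion may be restarted under careful nursing monitoring at one-half the previous rate".
- Moderate branch: "Stop the infusion until all symptoms resolve. If resolution occurs in less than 30 minutes, the infusion may be restarted under careful nursing monitoring", again at half the previous rate.

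Both branches let the physician order concomitant medication.

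Three other sections bear on the point. Protocol 3.3.1.1 says that the infusion "should be started within 3 hours of study drug reconstitution". Protocol 3.8 allows withdrawal where the investigator thinks that "continuation in the study would be detrimental to the" subject's well-being, or where an adverse event calls for it. Protocol 3.3.3.5 requires that "Reasons for any deviation from the administration of less than 100% of the investigational product dose" be recorded in the eCRF and the medical records.

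**The concern.** A safety algorithm graded by severity would normally be at least as strict for the graver reaction. Here the two checkable conditions, complete resolution and a time limit, appear only in the moderate branch. Followed as written, the section lets a subject be re-exposed after a severe reaction whose symptoms took longer to settle than would be allowed after a moderate one.

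The product is derived from human plasma and is given as a single dose right after anesthesia induction, just before major surgery. Protocol 3.2.2 excludes anyone with a history of anaphylaxis to blood or blood components, so the protocol itself treats this hazard as serious. With 35 centers planned, discretion without a common minimum may also be applied differently from site to site. What is at stake is the safety of individual subjects, not the trial's inference.

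**Working it through.** There is no plan figure to reproduce. The main check is a comparison of the two branches of 3.3.3.4.

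| Condition for restart | Moderate reaction | Severe reaction |
|---|---|---|
| State of symptoms | All resolved | Subsided |
| Time limit | Less than 30 minutes | None |
| Physician's discretion on restart | Not named | Named |
| Rate on restart | Half the previous rate | Half the previous rate |
| Nursing monitoring | Yes | Yes |

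The branches differ in three rows. The severe branch gains a named physician decision and lacks the two fixed floors. For example, a moderate reaction that clears fully at 40 minutes does not meet the restart condition. A severe reaction that has subsided at 40 minutes does, if the physician agrees.

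The next step is to see whether another section supplies the floors.

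- Protocol 3.3.1.1: the 3-hour limit runs from reconstitution to the start of the infusion. It does not address a restart.
- Protocol 3.8: withdrawal rests on the investigator's opinion and sets no restart condition.
- Protocol 7.2: the investigator may deviate to remove an immediate hazard. This permits caution but sets no floor.
- SAP: no restart or infusion-stopping rule.

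The size can only be illustrated, because the documents give no reaction rate. The planned AT-III arm is 202 (Protocol 5.2). The rates below are assumptions.

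- Severe reactions, at an assumed 0.1% to 1%: 202 × 0.001 = 0.20, to 202 × 0.01 = 2.02 subjects. This is an upper bound on those affected. The gap matters only if dose remains to be given, symptoms are unresolved or took 30 minutes or more, and the physician chooses to restart.
- Subjects affected, if an assumed 10% to 50% of severe reactions meet all three conditions: 202 × 0.001 × 0.10 = 0.02, to 202 × 0.01 × 0.50 = 1.01.
- Chance of at least one: 1 − (1 − 0.0001)^202 = 2.0%, to 1 − (1 − 0.005)^202 = 63.7%.

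The window for a reaction during infusion is probably short. The dose is 20 / 1.4 = 14.29 IU/kg. The documents do not give the strength after reconstitution, so take 25, 50 and 100 IU/mL undiluted as assumed values. The volumes are then 0.571, 0.286 and 0.143 mL/kg. The first 5 minutes deliver 5 × 0.05 = 0.25 mL/kg, which gives:

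- 25 IU/mL: 5 + (0.571 − 0.25) / 0.1 = 8.2 minutes
- 50 IU/mL: 5 + (0.286 − 0.25) / 0.1 = 5.4 minutes
- 100 IU/mL: 0.143 / 0.05 = 2.9 minutes

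Dilution would lengthen these times.

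**The case against.** The strongest reply is that the branches differ in kind, not in strictness. A fixed rule suits the milder, more predictable event, and a physician's case-by-case decision suits the graver one. The subject is already under anesthesia care, known anaphylaxis to blood products and excipient allergies are excluded, and a physician who declines to restart is fully compliant. *Subside* can also be read as settled. The Investigator's Brochure and the pharmacy manual, which may carry further guidance, are not among the documents reviewed. Finally, nothing in the documents shows that 30 minutes is the right limit for a severe reaction.

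Much of this stands. The discretion is a real gate, the symptom-state difference is partly a matter of reading, and harm would need a physician to choose re-exposure. But discretion replaces the fixed floors where it could have been added to them, and the documents give no reason why the graver reaction needs fewer. The missing time limit does not depend on how *subside* is read. Thirty minutes is simply the protocol's own limit for the milder event, so it is a natural outer bound for the severe one.

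A reader might infer that easing of symptoms alone is enough to restart after a severe reaction, or that the protocol calls for re-exposure. The documents support neither. Restart is expressly subject to the physician's decision, and the wording permits it without requiring it.

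**Conclusion.** The point holds in this limited form: the fixed floors of full resolution and less than 30 minutes apply only to the moderate reaction, and nothing else in the protocol or SAP extends them to the severe one. The absence of a time limit is certain. The absence of a full-resolution requirement is certain as to wording, but its practical weight depends on how *subside* is read.

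The number of subjects affected is unknown and probably very small. The illustrative 0.02 to 1.0 subjects rests wholly on assumed rates, and the range is too wide to carry weight. The base of 202 is also generous, because it counts randomized subjects and SAP section 13 reports more undosed subjects than expected. No conclusion about harm follows from these figures.

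The endpoint, alpha, power and analysis populations are unaffected. This is a cheap improvement to patient safety.

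**What to change.** In the severe branch of Protocol 3.3.3.4, keep the physician's discretion and add the moderate branch's own conditions. Suggested wording: *After a severe reaction, stop the infusion. Only if all symptoms have resolved in less than 30 minutes may the physician decide to restart, at half the previous rate and under careful nursing monitoring.* Leave the moderate branch unchanged. The severe branch is then at least as strict as the moderate one.

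The cost is a wording change and a memo to sites, with no added procedures or subjects. The downside is at most a few incomplete doses: no more than the 0.2 to 2.0 severe reactions in the AT-III arm at the assumed rates. Protocol 3.3.3.5 already captures the reasons for an incomplete dose, so no new data field is needed. Under SAP 5.2 these subjects stay in the safety population and, if operated on, in the mITT population, because both require only that some study drug was given.

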3.3.3.5 Treatment Compliance

Treatment compliance will be measured only in terms of the subject receiving an infusion of AT-III (Human) from the study personnel. No other measure of treatment compliance will be employed.

Reasons for any deviation from the administration of less than 100% of the investigational product dose as prepared by the pharmacist, or designee, must be recorded in the electronic case report form (eCRF) and in the subject's medical records.

3.4 Prior and Concomitant Therapy

Concomitant medications and those taken within the last month (including transfusions of blood or any blood-derived product) prior to the Screening visit must be recorded in the eCRF, including the trade or generic names of the medication, the dose, the route of administration, and the duration of the medication (frequency).

3.4.1 Prior to Study Treatment

Subjects may be on heparin or low-molecular weight heparin, and vitamin K antagonists if international normalized ratio (INR) <1.3 on the day of surgery. Prior treatment with Clopidogrel and Ticagrelor must be discontinued at least 5 days before surgery. Prior treatment with Prasugrel must be discontinued at least 7 days before surgery. Glycoprotein IIb/IIIa receptor blockers must be discontinued at least 24 hours before surgery.

3.4.2 Concomitant Medications during the Study

Concomitant administration of heparin, low-molecular weight heparin, coumadin, tranexamic acid, aminocaproic acid, desmopressin, and recombinant activated factor VII (rFVIIa) may be used in order to avoid thrombotic risk.

Details of any concomitant medication must be recorded on the eCRF except for anesthesia related products, fluid replacement therapies, and electrolyte supplementation.

In addition, products given at different doses on the same day to manage and maintain vital functions (e.g. insulin, furosemide) will only be recorded once on the eCRF and dosage will be reported as PRN (pro re nata).

In the event that an AE or suspected adverse drug reaction (ADR) should occur, complete details of all concomitant medication will be reported to the sponsor.

3.4.3 Prohibited Concomitant Medications during the Study

Tirofiban, abciximab, and eptifibatide may not be used during this clinical trial.

3.5 Study Variables

3.5.1 Efficacy Variables

1. Percentage of subjects with any component of a **major morbidity composite** defined as a composite of any one or more of the following events (up to Day 30±4 days):
 - a. Postoperative **mortality** (defined as all deaths occurring within 30 days of the operation or occurring during the primary hospitalization).
 - b. **Stroke** (defined as a clinical diagnosis of focal or global neurological deficit of abrupt onset caused by a disturbance in cerebral blood supply).
 - c. **Acute kidney injury** (defined as an increase of serum creatinine levels to >2.0 mg/dL and twice the baseline level or a new requirement for dialysis postoperatively).
 - d. **Surgical reexploration** (defined as having to return to the operating room because of bleeding, tamponade, graft occlusion or any other cardiac reason).
 - e. **Arterial or venous thromboembolic event** (consisting of perioperative MI, mesenteric infarction, peripheral thromboembolism, acute coronary graft thrombosis, intracardiac thrombosis, deep vein thrombosis [DVT], and pulmonary embolism).
 - f. **Prolonged mechanical ventilation** (defined as mechanical ventilation >24 hours).
 - g. **Infection** (defined as presence of deep sternal-wound infection and/or bloodstream infections).

2. AT activity (levels) determinations:

- a. AT activity levels will be measured for both AT-III (Human) treatment and Placebo control groups at a central lab (unless specified at local lab) for the following time points:
 - Prescreening visit (local lab)*
 - Screening visit (local lab)* §
 - Screening visit
 - Preoperatively
 - Immediately before study drug administration
 - Immediately after study drug administration
 - Postoperatively at ICU admission
 - Postoperatively Day 1
 - Postoperatively Day 2
 - Postoperatively Day 3
 - Postoperatively Day 5
 - ICU discharge
 - 1-month follow-up visit

* Only applicable for subjects undergoing isolated CABG or single valve repair/replacements (will be needed for eligibility only if subject not receiving preoperative heparin [see entry criteria]).

§ This AT (local lab) determination will not be required if the Prescreening visit is conducted.

- b. Percentage of subjects with AT levels of 58% or higher at the ICU admission will be calculated for both treatment groups and compared.

All AT measurements will be performed on a central venous catheter blood sample, if the central venous catheter is already in place, through a calibration curve prepared by serial dilution of the human normal plasma pool and expressed as a percentage of activity. If a central venous catheter is not already in place, peripheral blood sample will be used for measuring AT levels.

3. Chest-drain blood loss (mL) will be measured within the first 12 and 24 hours of chest closure.

Chest-drain blood loss in the first 12 and 24 hours is defined as the amount of blood collected in the cardiotomy reservoir from chest closure through the following 12 and 24 hours measured.

4. **Transfusion requirements** will be measured as the number of units of Fresh frozen plasma (FFP), red blood cells (RBCs), platelets (PLTs), cryoprecipitate/fibrinogen, prothrombin complex concentrates (PCCs), from the day of ICU admission and throughout the follow-up period.

A specific perioperative transfusion algorithm will be applied:

Standardized Transfusion Algorithm

Red blood cells:

Administration of RBCs should be performed one unit at a time after which the hemoglobin (Hb) levels should be reanalyzed to check the suitability for the next unit.

- Hb <6.0 g/dL (≤ 3.72 mmol/L [millimoles/liter]): Transfusion is mandatory
- Hb = 6.0-8.0 g/dL (3.72-4.96 mmol/L): Transfusion is optional
- Hb = (8.0-10.0 g/dL). Transfusion is acceptable only if clinically justified*
- Hb >10.0 g/dL: Transfusion is not permitted.

* One or more of the following clinical justifications must be provided:

- Central venous saturation (Swan Ganz / Central Venous Pressure (CVP) <60% with an arterial oxygen saturation of at least 90%.
- Cardiac Index (CI) <2.0 unresponsive to inotropic or mechanical support (catecholamine, intra-aortic balloon pump [IABP], etc.).
- Signs / symptoms of organ ischemia, such as: change in ST-segment or left ventricular wall motion abnormalities (LV).

Coagulation products:

Only if subject is bleeding 4 mL/kg/hour or more over at least 30 minutes or 1.5 mL/kg/hour or more over 2 consecutive hours.

- Fresh frozen plasma (10-15 mL/kg) / Prothrombin complex concentrates: If subject is actively bleeding and presents an INR ≥ 1.5 .
- Platelets: 1 apheresis unit or 4-6 pooled units if the PLT count is <100,000/ μ L.
- Cryoprecipitate / Fibrinogen concentrates: Administration of 8-10 units of cryoprecipitate or 2 grams of fibrinogen concentrate if the concentration of fibrinogen ≤ 1.5 g/L.

Shed blood collected during surgery can be retransfused according to institutional practice. Retransfusion of chest-drain collected blood is not permitted.

5. Percentage of subjects needing **surgical reexploration** defined as having to return to the operating room because of bleeding, tamponade, graft occlusion or any other cardiac reason will be considered from chest closure to the end of the follow-up period.
6. Percentage of subjects with **low cardiac syndrome** defined as the need for major inotropic support or intra-aortic balloon pump will be considered from the day of ICU admission and throughout the follow-up period.
7. Percentage of subjects with postoperative **myocardial infarction** defined through enzymatic criteria plus new Q-waves at the electrocardiogram (ECG) will be considered from the day of ICU admission and throughout the follow-up period.

A perioperative MI is diagnosed by the following criteria:

(0-24 hours postoperation):

The CK-MB (or CK if MB not available) must be greater than or equal to 5 times the upper limit of normal with or without new Q waves present in two or more contiguous ECG leads. No symptoms required.

(>24 hours postoperation): Documented by at least one of the following criteria:

- a. Evolutionary ST-segment elevations
- b. Development of new Q-waves in two or more contiguous ECG leads
- c. New or presumably new left bundle branch block (LBBB) pattern on the ECG
- d. Creatine phosphokinase-MB isoenzyme (CK-MB) (or CK if MB not available) ≥ 3 times the upper limit of normal

8. Percentage of subjects with postoperative **stroke** defined as a clinical diagnosis of focal or global neurological deficit of abrupt onset caused by a disturbance in cerebral blood supply will be considered from the day of ICU admission and throughout the follow-up period.
9. Percentage of subjects with **acute kidney injury** defined as an increase of serum creatinine levels to >2.0 mg/dL and twice the baseline levels or new requirement for dialysis postoperatively, will be considered from the day of ICU admission and throughout the follow-up period. A new requirement for postoperative dialysis may include hemodialysis, peritoneal dialysis, and any form of ultrafiltration.
10. Percentage of subjects with **arterial or venous thromboembolic events** defined as perioperative MI, stroke, mesenteric infarction, peripheral thromboembolism, acute coronary graft thrombosis, intracardiac thrombosis, deep vein thrombosis [DVT], and pulmonary embolism, will be considered from the day of ICU admission and throughout the follow-up period.

11. Percentage of subjects with **infections** defined as presence of deep sternal-wound infections involving muscle, bone or mediastinum or bloodstream infections from the day of ICU admission and throughout the follow-up period.

The diagnosis of infection must have at least one of the following conditions:

- a. Wound opened with excision of tissue or reexploration of the mediastinum
- b. Positive culture
- c. Treatment with antibiotics

12. Percentage of subjects with **prolonged mechanical ventilation** defined as the need for mechanical ventilation >24 hours from the day of ICU admission and throughout the follow-up period.

13. Percentage of subjects with **all-cause postoperative mortality** defined as death during the same hospitalization as surgery or after discharge and throughout the follow-up period.

14. **ICU stay** duration (days) will be measured from the ICU admission. If duration is greater than the follow-up period, >1 month will be recorded.

15. Percentage of subjects with **prolonged ICU stay** defined as >6 days will be considered from ICU admission during a maximum of 34 days.

16. **Length of hospital stay** (days) in both groups defined as the discharge date minus the surgery date plus 1 day, during a maximum of 34 days after ICU admission. If this time interval is greater than the follow-up period, >1 month will be recorded.

